3.5.4 Drug Administration

When the decision is made to proceed with induction of labor for preeclampsia, and after ensuring for a consented patient, an order to give the study medication will be activated and the available study medication will be administered by the provider. The patient is considered randomized once the medication is dispensed. The investigational drug pharmacy will deliver the next study medication to the labor and delivery unit if a subsequent consented patient is already identified.

3.5.5 Baseline Procedures

- Routine intrapartum and postpartum care at each center will be provided to patients by their clinical providers who will be blinded to the study interventions.
- Trained and experienced research nurses in obstetric and perinatal outcomes abstraction at each center (also blinded to study medications) will be responsible for research data abstraction from patient medical records

Maternal and delivery outcomes will be collected during hospital stay. Occurrence of medication adverse effects or any of the pre-specified outcomes will be recorded by review of medical records by research nurses.

4. Outcome Measures

4.1 Primary Outcome: The primary outcome of the study is rate of cesarean delivery

4.2 Secondary outcomes:

- a. Time to active labor (defined as dilatation 5 cm or greater),
Delivery within 12 hours
Delivery within 24 hours
Maternal length of stay (defined as length of time from admission for induction to discharge postpartum, days)
Indication for cesarean delivery
Need to treat with acute antihypertensive medications
Uterine hyperstimulation (either a series of single contractions lasting 2 minutes or more OR a contraction frequency of five or more in 10 minutes)
Maternal hypotension (Symptomatic with blood pressure systolic of less than 90 millimeters of mercury (mm Hg) or diastolic of less than 60 mm Hg)
- b. Maternal side-effects (headache, nausea, vomiting, dizziness, or any other unexpected adverse effect)

A composite maternal morbidity outcome is pre-specified to include one or more of the following during labor, delivery, or in the immediate postpartum during admission:

- third- or fourth-degree perineal laceration
- blood transfusion
- endometritis
- wound separation–infection (defined by the need for additional wound closure or the need for antibiotics)
- hysterectomy
- intensive care unit admission
- maternal death

Other maternal secondary outcomes analyzed will be:

- placental abruption
- chorioamnionitis (defined by the presence of maternal fever 100.4°F or greater in the presence of maternal or fetal tachycardia or fundal tenderness)
- use of terbutaline
- intrauterine pressure bulb
- amnioinfusion
- analgesia use

A composite neonatal morbidity outcome is pre-specified to include one or more of the following before neonatal discharge:

- severe respiratory distress syndrome (defined as intubation and mechanical ventilation for a minimum of 12 hours), culture proven presumed neonatal sepsis
- neonatal blood transfusion

- hypoxic–ischemic encephalopathy
- intraventricular hemorrhage grade 3 or 4
- necrotizing enterocolitis
- receipt of head cooling
- Other neonatal outcomes analyzed will be neonatal intensive care unit admission, neonatal intensive care unit admission greater than 48 hours, and neonatal length of stay (days).

5. Statistical Considerations

5.1 Sample size calculation:

Using data from our prior studies using the intended study population at The Ohio State Wexner Medical Center the incidence of gestational hypertension or preeclampsia is 10-15%.

Data abstracted from those enrolled in biorepository for gestational hypertension or preeclampsia over one year period and excluding those who were delivered for gestational hypertension or preeclampsia who had cesarean section for breech, prior cesarean section or uterine surgery, HELLP syndrome, eclampsia.

295 women underwent induction of labor for gestational hypertension or preeclampsia 48% (n=141) ended up with cesarean delivery after failed induction of labor or non-reassuring fetal well being.

Gestational Age Distribution for Gestational Hypertension or Preeclampsia Induction

Gestational Age in weeks	Number of women IOL for gHTN or PE	CS rate
24-28 wks	13	10 (77%)
28-30 wks	15	11 (73%)
30-32 wks	26	18 (69%)
32-34 wks	39	19 (49%)
34-36 wks	56	20 (34%)
36-37 wks	35	12 (34%)
37-38 wks	57	22 (38%)
38-39 wks	17	3 (18%)
39-40 wks	8	2 (25%)
40-41 wks	2	1 (50%)

Review of literature reveals is similar to OSU numbers, with the overall rate of cesarean delivery after induction of labor for gestational hypertension or preeclampsia ranges from 40% to 70%. Based on available data, we anticipate that the expected rate of the primary outcome in the women undergoing induction of labor for gestational hypertension or preeclampsia 45%. For this proposal, we will estimate a conservative relative reduction effect of 30-35%.

The table below provides the sample size calculations needed to achieve 80-90% power to detect 30-35% difference in the primary outcome between women receiving IMN or placebo at time of their induction of labor for preeclampsia, using a two-tailed alpha of 0.05.

Table 1. Total sample size required to detect a difference in primary outcome in women undergoing induction of labor and receiving IMN or placebo (alpha at 0.05, variable primary outcome rates, power, and effect sizes)

Relative reduction (%)	Power (%)	Primary Outcome Rate in Placebo group				
		35%	40%	45%	50%	55%
30	90	784	644	540	462	380
	85	670	550	460	394	326
	80	586	480	404	346	284
33	90	656	540	430	368	306
	85	562	462	368	316	276
	80	490	404	322	276	242
35	90	586	482	406	330	290
	85	502	412	348	282	248
	80	438	362	304	248	216

Assuming the primary outcome to be 45 %, close to 1:1 enrollment and anticipating that no more than 2% of randomized women to be lost to follow up, a sample size of 400 women will achieve >85% power to detect a 33% relative reduction in primary outcome overall.

Given the study design and that randomization will occur once decision to proceed with induction occurs, there will be no concern for loss to follow up or missing outcome data on any women. Regarding concern for non-compliance, given study design we propose that it is unlikely that participant would not get their assigned treatment.

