Specific aim 3: To evaluate the safety of NOD isosorbide mononitrate (IMN) administered at the time of induction of labor in terms of frequency of intrapartum outcomes including placental abruption, need to treat with acute antihypertensive

medications, uterine hyperstimulation, maternal hypotension, atony, side effects (headache, nausea, vomiting, dizziness), and neonatal resuscitation.

3. Study Design

3.1 Primary Research Question:

Does intravaginal administration of NOD isosorbide mononitrate (IMN) as an adjuvant to misoprostol/ intra-cervical Foley bulb for induction of labor decrease the rate of cesarean deliveries in pregnancies complicated by gestational hypertension or preeclampsia?

Hypothesis 1: Compared to placebo, administration of intravaginal IMN as adjuvant to induction of labor decreases rate of cesarean deliveries in pregnancies complicated by gestational hypertension or preeclampsia.

3.2 Secondary Research Questions:

3.2.1 Does use of intravaginal NOD isosorbide mononitrate (IMN) as an adjuvant to misoprostol/ intra-cervical Foley bulb for induction of labor reduce the interval time to delivery?

Hypothesis 2: Compared to placebo, administration of intravaginal IMN at the time of induction of labor reduces the time interval from induction to vaginal delivery.

3.2.2 Is use of intravaginal IMN as an adjuvant induction agent in pregnancies complicated by preeclampsia associated with a favorable risk/benefit ratio?

Hypothesis 3: Administration of intravaginal IMN as an induction agent is safe and not associated with an increased risk of placental abruption, use of anti-hypertensives, maternal hypotension and uterine hyperstimulation, atony, meconium stained fluid compared to placebo, need for neonatal resuscitation.

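### Headache, nausea, vomiting and dizziness are named safety outcomes, but the only stated source is the medical record, so their rates and risk differences are likely to be understated.

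*Combined protocol and SAP*

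**What the plan says.** Section 3.5.5 gives one method of ascertainment for adverse effects: "Occurrence of medication adverse effects or any of the pre-specified outcomes will be recorded by review of medical records by research nurses". The research nurses, who are blinded, "will be responsible for research data abstraction from patient medical records". On timing, the same section says "Maternal and delivery outcomes will be collected during hospital stay".

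The symptoms concerned are named twice. Specific aim 3 (section 2.0) ends its list with acute antihypertensive "medications, uterine hyperstimulation, maternal hypotension, atony, side effects (headache, nausea, vomiting, dizziness), and neonatal resuscitation". Section 4.2, item b, makes them a secondary outcome: "Maternal side-effects (headache, nausea, vomiting, dizziness, or any other unexpected adverse effect"). The section on reported adverse reactions (the second section numbered 6.1) lists headache, nausea and hypotension for the study drug, with vomiting and vertigo as less frequent.

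No section provides a symptom questionnaire, a checklist, a fixed assessment time, a pre-dose symptom record or a severity grade. No section says how to code a chart that is silent on a symptom, and section 5.1 expects no missing outcome data. Section 5.5 describes the analysis of secondary outcomes only in general terms, with no effect measure for safety.

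**The concern.** Chart review suits cesarean delivery, transfusion or intensive care admission, because such events generate a record. A headache or a spell of dizziness enters the chart only if the woman mentions it and someone writes it down. If no missing data are expected and there is no code for a symptom that was not assessed, a silent chart will probably be scored as no symptom.

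At stake is the cost side of the risk/benefit question in section 3.2.2. The rates reported to clinicians would be too low, the excess on active drug would look smaller than it is, and a real excess would more often be non-significant. Section 5.2 also puts emphasis on maternal safety outcomes at interim review, so the same loss would weaken monitoring. Symptoms that were never charted cannot be recovered later.

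**Working it through.** **Inputs from the plan (section 5.1).** Total 400 women, about 1:1, at most 2% lost, two-sided alpha 0.05. Hence 400 × 0.98 / 2 = 196 per arm.

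**Inputs assumed.** The plan gives no side-effect rate and no charting completeness. Let s be the fraction of true cases that are charted, equal in both arms, with no false positives. True rates of 20% v 35% and 20% v 40% (placebo v active) are illustrations only.

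**Power formula.** Power = Φ[(d − 1.96·SE0) / SE1], where d is the difference in proportions, SE0 = √[2·p̄(1−p̄)/n] and SE1 = √[p1(1−p1)/n + p2(1−p2)/n].

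**The plan's own figure first.** For cesarean delivery, 45% v 45% × 0.67 = 30.15% gives power of 86.2% at 196 per arm and 86.9% at 200. The stated figure of more than 85% reproduces. It is the only power claim in the plan; none is made for side effects.

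**Under-charting.** Observed rates are s·p1 and s·p2. The risk difference becomes s(p2 − p1), while the risk ratio s·p2 / s·p1 is unchanged.

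- 20% v 35%, s = 1: d = 0.15, SE0 = 0.0451, SE1 = 0.0445. (0.15 − 0.0884)/0.0445 = 1.38, so power is 92%.
- 20% v 35%, s = 0.5: 10% v 17.5%, d = 0.075, SE0 = 0.0348, SE1 = 0.0346. (0.075 − 0.0682)/0.0346 = 0.20, so power is 58%.

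| True rates | Charted fraction | Observed rates | Risk difference (points) | Power | Risk ratio (approx. 95% interval) |
|---|---|---|---|---|---|
| 20% v 35% | 100% | 20% v 35% | 15 | 92% | 1.75 (1.25–2.46) |
| | 70% | 14% v 24.5% | 10.5 | 75% | 1.75 (1.14–2.68) |
| | 50% | 10% v 17.5% | 7.5 | 58% | 1.75 (1.04–2.94) |
| 20% v 40% | 100% | 20% v 40% | 20 | 99% | 2.00 (1.44–2.78) |
| | 70% | 14% v 28% | 14 | 93% | 2.00 (1.32–3.02) |
| | 50% | 10% v 20% | 10 | 79% | 2.00 (1.21–3.31) |

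The intervals use SE(log RR) = √[(1−p1)/(n·p1) + (1−p2)/(n·p2)] at the expected rates.

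**False positives.** If a woman without a true event can be recorded as having one (for example, a symptom that predates the study drug), the ratio shrinks too. With true rates of 10% v 20%, 50% sensitivity and 95% specificity, the observed rates are 0.5 × 0.10 + 0.05 × 0.90 = 9.5% and 0.5 × 0.20 + 0.05 × 0.80 = 14%, a ratio of 1.47 instead of 2.0.

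**Unequal charting.** The direction for the ratio is then not fixed. With true rates of 20% v 40%, charting 50% on placebo and 60% on active drug gives 10% v 24%, a ratio of 2.4; charting 50% and 40% gives 10% v 16%, a ratio of 1.6.

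**The case against.** The best defense is that this is a blinded trial sized for cesarean delivery, and that the plan claims no power for side effects. Providers and abstractors are both blinded, so charting should be about equal in the two arms. With equal sensitivity and no false positives the risk ratio is unbiased. A large excess would still be found: at 20% v 40% with half the cases charted, power is 79%. All of this stands. It limits the point to understated absolute rates, a smaller risk difference, lower power and a wider interval for the ratio.

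A reader might infer more than the documents support:

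- **That the review is retrospective and that uncharted symptoms are scored as absent by rule.** The plan says collection takes place during the hospital stay and states no coding rule. Scoring as absent is a likely consequence, not a stated one. Collection during the stay does not help, however, if the source is still the chart.
- **That nobody asks about symptoms.** The plan is silent on what bedside staff ask in routine care. What can be said is that it does not require anyone to ask.
- **That the comparison is necessarily biased toward no increase.** On the ratio scale it need not be, and unequal charting could push either way, though blinding makes that less likely.
- **That the result is driven toward Hypothesis 3.** That hypothesis begins "Administration of intravaginal IMN as an induction agent is safe and not associated with an increased risk of placental abruption", and its list does not contain headache, nausea, vomiting or dizziness. The one listed outcome that may depend on symptom charting is hypotension, which section 4.2 defines as "Maternal hypotension (Symptomatic with blood pressure systolic of less than 90 millimeters of mercury (mm Hg") or a low diastolic value.

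**Conclusion.** The concern holds in a limited form. Medical-record review is the only stated source for four subjective symptoms that the plan names as safety outcomes, and active questioning is not provided for. Under-recording would lower the reported rates and the risk difference in proportion to the charted fraction. In the illustration, a true 15-point excess would appear as 10.5 points at 70% charting and 7.5 points at 50%, with power falling from 92% to 75% and 58%.

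The size rests entirely on assumed rates and charting fractions, on equal charting in both arms, on no false positives, and on silent charts being read as negative. The finding bears on Specific aim 3, secondary outcome b and the risk/benefit question in section 3.2.2. This is a cheap improvement to a secondary safety measurement and should be made; it is not a contradiction within the plan.

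**What to change.** In section 3.5.5, for headache, nausea, vomiting and dizziness, add a blinded checklist with three codes: present, absent, not assessed.

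- **When:** before the first study dose, at each later study-drug administration, and once after the last dose at a routine contact. Section 3.5.4 already has a provider at the bedside when the drug is given ("the available study medication will be administered by the provider"). Under section 3.3 study drug may stop before three doses, and no 4-hourly attendance is guaranteed for every woman afterward, so the form should follow actual administrations rather than a fixed clock.
- **Event definition:** a symptom that is new since the pre-dose record, so that pre-existing symptoms are not counted.
- **Analysis (section 5.5):** report risk differences and risk ratios with 95% confidence intervals for each symptom, and the number not assessed by arm.
- **Unchanged:** chart review for all other outcomes and for unexpected effects. Hypotension therefore still depends on how symptoms are charted. No dose, schedule or treatment rule changes.

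The cost is a few more data fields and a brief question during labor, asked by staff who already attend. Reported rates will rise in both arms, and prompting will bring in some symptoms unrelated to study drug. Those act as false positives and pull the ratio toward 1; the pre-dose record removes only the ones present beforehand.

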6.0 Medication

6.1 Study drug: Isosorbide mononitrate is a drug used principally in the treatment of angina pectoris and acts by dilating the blood vessels so as to reduce the blood pressure. Research on extended release Isosorbide mononitrate as a cervical ripener to reduce time at hospital to birth is supportive. Isosorbide mononitrate is an active metabolite of isosorbide dinitrate and exerts qualitatively similar effects. It reduces the workload of the heart by producing venous and arterial dilation. By reducing the end diastolic pressure and volume, isosorbide mononitrate lowers intramural pressure, hence leading to an improvement in the subendocardial blood flow. The net effect when administering isosorbide mononitrate is therefore a reduced workload for the heart and an improvement in the oxygen supply/demand balance of the myocardium.

For purpose of this study 30mg Isosorbide mononitrate suppositories and matching placebo have been compounded by an investigational pharmacy using using a commercial extended release tablets formulated into suppositories by SBH Medical and IDS an investigational pharmacy will manage the storage and dispensing. A prototype suppository was used to determine feasibility. Potency testing was performed to get initial baseline then rechecked in 90 days, the results supported the shelf life and proof of concept (potency) on the suppositories. Per State Board of Pharmacy, Investigational Drug Service are not allowed to possess more than 7 days worth of non-patient specific compounded medication, and given our expected enrollment of approximately 5-6 patients per week, they will store 20 tablets of compounded medication/placebo. Suppositories will be refrigerated, and BUD is 30 days, protected from light and moisture.

The suppositories are manufacturer by:
SBH Medical, Ltd
[name] R.Ph. ([contact])
[name]
[contact]; [contact]
Web:

And will be stored at:
Investigational Drug Service
[name]
[name]
[name]

6.1 Reported adverse reactions:

Headache
Tiredness
Sleep disturbances
Gastrointestinal disturbances
Hypotension
Poor appetite
Nausea

Other reactions that have been reported less frequently with isosorbide mononitrate modified release tablets include tachycardia, vomiting, diarrhea, vertigo and heartburn

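### A low blood pressure without charted symptoms is never counted as maternal hypotension, so the safety comparison can miss a real fall

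*Combined protocol and SAP*

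**What the plan says.** Section 4.2 lists maternal hypotension as a secondary outcome and defines it as "Symptomatic with blood pressure systolic of less than 90 millimeters of mercury (mm Hg) or diastolic of less than 60 mm Hg". The natural reading applies the symptom requirement to both thresholds. The definition does not say which symptoms qualify, whether they must be attributed to the low pressure, or how close in time they must be.

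The questions this outcome serves carry no such limit. Specific aim 3 (Section 2.0) lists "uterine hyperstimulation, maternal hypotension, atony, side effects (headache, nausea, vomiting, dizziness), and neonatal resuscitation" among the safety outcomes. Hypothesis 3 (Section 3.2.2) states that the drug "is safe and not associated with an increased risk of placental abruption, use of anti-hypertensives, maternal hypotension and uterine hyperstimulation".

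Section 6.1 says that IMN "acts by dilating the blood vessels so as to reduce the blood pressure" and includes hypotension, headache and nausea among its reported reactions, with vomiting and vertigo as less frequent ones. Section 4.2 separately lists headache, nausea, vomiting and dizziness as maternal side effects. Section 3.5.5 has blinded research nurses abstract outcomes from the medical record. The documents give no schedule for measuring blood pressure and no symptom checklist.

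**The concern.** The outcome is narrower than the question. For a vasodilator given to women who may also receive acute antihypertensives (Section 6.2 warns that such drugs can add to the effect), a fall in pressure is a central expected harm. A woman with a low reading and no charted symptom does not meet the definition. Section 4.2 has no outcome based on readings alone and no continuous blood pressure outcome. Need for acute antihypertensive treatment responds to high pressure, not low.

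Hypothesis 3 is worded as an absence of increased risk, and Section 5.5 offers only a two-group comparison. An outcome that discards some of the low readings makes a non-significant result more likely, and such a result could be taken as support for safety. Section 5.2 also gives maternal safety outcomes particular weight at the interim reviews.

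**Working it through.** **Inputs from the documents.** Total 400, 2% loss, 1:1 allocation, two-sided alpha 0.05 (Sections 3.5.3 and 5.1). Evaluable women: 400 × 0.98 = 392, or 196 per arm.

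**Inputs assumed.** The documents give no rate of readings below the thresholds and no symptom rate. Both are varied below.

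**Formula.** With rates p1 and p2, n per arm and p̄ = (p1 + p2)/2:
- S0 = √[2p̄(1 − p̄)/n]
- S1 = √[(p1(1 − p1) + p2(1 − p2))/n]
- power = Φ[(|p2 − p1| − 1.96 × S0)/S1]

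**Step 1: the plan's own figure.** Section 5.1 claims more than 85% power for cesarean delivery at 45% with a 33% relative reduction. The treated rate is 0.45 × 0.67 = 30.15%. Then (0.1485 − 1.96 × 0.04892)/0.04834 = 1.088, giving 86.2%. The claim reproduces, so the formula suits the plan. It says nothing about hypotension, for which the plan states no power.

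**Step 2: low readings without symptoms.** If a proportion b of an arm has a low reading and a fraction s of those women have symptoms, the counted rate is b × s. Take b = 10% (placebo) and 20% (IMN), with s equal in both arms.
- Readings alone: (0.10 − 1.96 × 0.03607)/0.03571 = 0.82, power 79%.
- s = 30%, counted 3% versus 6%: (0.03 − 1.96 × 0.02094)/0.02089 = −0.53, power 30%.

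| Low readings, placebo vs IMN (assumed) | Readings alone | s = 50% | s = 30% | s = 20% |
|---|---|---|---|---|
| 5% vs 10% | 47% | 26% | 17% | 13% |
| 10% vs 20% | 79% | 47% | 30% | 21% |
| 15% vs 30% | 95% | 65% | 43% | 30% |

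Exact binomial calculation changes these entries by less than two percentage points.

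**Step 3: unequal symptom fractions.** Suppose pressure is identical in the two arms, drug symptoms qualify, and symptoms are independent of pressure. The counted relative risk is then (b × s_IMN)/(b × s_placebo) = s_IMN/s_placebo, whatever b is. The chance of a significant excess under IMN (exact, 196 per arm) depends heavily on the assumptions:
- 5% low readings, symptoms 40% versus 20%: 2% versus 1% counted, about 4 versus 2 women, chance 11%.
- 30% low readings, symptoms 50% versus 20%: 15% versus 6% counted, chance 84%.

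On readings alone the relative risk is 1.0, and the chance of a significant excess is at most about 2.5%.

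**The case against.** Symptomatic hypotension is a legitimate and clinically relevant safety outcome, and replacing or demoting it would be a matter of preference. That stands, and the fix keeps it. Hypotension may also reach the trial record as a charted medication adverse effect, and side effects are reported separately, so an imbalance in headache would be visible. This helps in part, but neither route systematically counts low readings without symptoms.

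A reader might infer that the definition will manufacture a hypotension harm from nitrate headache. The documents do not support that. The definition names no symptom; the overlap with drug effects is inferred from the lists in Sections 4.2 and 6.1. The term ordinarily means symptoms attributed to the low pressure. Headache alone can never count, because a reading below a threshold is also required, in women being induced for hypertensive disease. Every counted woman would have a low pressure; only the difference between arms could mislead. What remains is that an undefined term permits this. Blinding would not prevent it, because the symptoms would be real drug effects.

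It is also fair to say that the two directions should not be claimed together. Step 2 assumes equal symptom fractions. With low readings of 10% versus 20% and symptoms in 20% versus 40% of those women, the counted rates are 2% versus 8%: (0.06 − 1.96 × 0.02202)/0.02181 = 0.77, power 78%, about the same as readings alone. The loss of power disappears, but the contrast then mixes symptoms with pressure.

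A reader might extend the argument to chorioamnionitis, since tachycardia is a listed reaction and one qualifying sign. Fever is still required there and is not a listed reaction, so that extension is not made.

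**Conclusion.** The concern holds for low readings without symptoms. This follows from the definition and needs no assumption: such readings are not counted, the aim and hypothesis would include them, and no other listed outcome is designed to capture them.

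The size is illustrative. With low readings doubled from 10% to 20% and equal symptom fractions of 50% down to 20%, power falls from about 79% to between 47% and 21%. Other assumed rates give the range in the table. If low readings are rare (5% versus 10%), even readings alone give only 47%, so the fix improves the comparison without guaranteeing an answer.

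The possible excess from drug symptoms is secondary. It rests on an undefined term, and its size cannot be settled from the documents. Neither point touches the primary cesarean comparison.

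**What to change.** In Section 4.2, keep symptomatic hypotension as it is and add a second outcome: any charted systolic below 90 or diastolic below 60 mm Hg, whether or not symptoms are recorded. Compare both between arms and report them side by side. State that *symptomatic* means symptoms recorded at the time of the low reading, and name the period over which readings count. The thresholds are the protocol's own; only the counting of outcomes changes, not care.

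The cost is a change of wording and a little more abstraction from records already under review, with no added patients or visits. The count based on readings alone will be higher and less specific, which is why the symptomatic outcome stays beside it.

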Recent evidence has emerged about the role that locally applied NO donors play in cervical ripening and that NO-donors are effective and safe cervical ripening agents. A recent Cochrane Database review of the existing evidence in humans suggest that NO donors can be a useful tool in the process of induction of labor causing the cervix to be more favorable in comparison to placebo. The authors concluded that, additional data are needed to assess the true impact of NO donors on all important labor process and delivery outcomes.

We hypothesize that using a NO donor as an adjuvant to misoprostol/ intra-cervical Foley bulb for induction of labor in women with gestational hypertension and/or preeclampsia will have a synergistic effect by ripening the cervix, and shortening the overall duration of labor. If our hypothesis is confirmed, this approach may represent a significant advancement in clinical care because it will potentially significantly decrease the rate of Cesarean delivery women with gestational hypertension or preeclampsia, where the rates of surgical interventions are very high. The existing evidence also implies the NO adjuvant method will be reducing maternal blood pressures, thereby decreasing the utilization of intrapartum anti-hypertensives.

Here, we propose a randomized controlled trial (RCT) of nitric-oxide donor (NOD) isosorbide mononitrate (IMN) versus placebo as an adjuvant to misoprostol/ intra-cervical Foley bulb for induction of labor to decrease rate of cesarean deliveries in pregnancies complicated by gestational hypertension or preeclampsia ($\geq 24/0$ weeks' gestation)

The primary outcome will be rate of cesarean delivery. Secondary outcomes include interval time to delivery, acute use of anti-hypertensives and incidence of maternal/neonatal complications associated with use of IMN, to the point of discharge/transfer.

2.0 Specific Aims:

Specific aim 1: To determine if intravaginal administration of NOD isosorbide mononitrate (IMN) as an adjuvant to misoprostol/ intra-cervical Foley bulb for induction of labor decreases the rate of cesarean deliveries in pregnancies complicated by gestational hypertension or preeclampsia ($\geq 24/0$ weeks' gestation)

Specific aim 2: To determine if the use of intravaginal administration of NOD isosorbide mononitrate (IMN) as an adjuvant to misoprostol/ intra-cervical Foley bulb for induction of labor reduces the interval time to delivery.

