3.4 Eligibility Criteria

3.4.1 Inclusion Criteria:

- Women older than 18 years at the time of induction of labor with the ability to give informed consent
- Induction of labor for clinical diagnosis of preeclampsia
- Unfavorable cervix (Bishop's score of less than 6) See below
- Cervical dilation 2cm or less
- Singleton
- Gestational age \geq 24 weeks
- English speaking

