5.2 Interim Analysis

Interim statistical analyses of clinical trials will be at least once a year to review trial results; however, the exact timing of the interim analyses is at the discretion of the PI. A formal detailed statistical report will be written by the PI which presents the results of every aspect of the study, including all baseline variables, protocol adherence, all outcome variables, adverse events reported and center performance in terms of recruitment, data quality, loss to follow-up and protocol violations. However, the main emphasis is on the primary outcome as well as maternal safety outcomes. It is recognized that any decision to terminate the study would not be reached solely on statistical grounds but on a number of complex clinical and statistical considerations.

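### Fetal death in labor and neonatal death are not listed outcomes, so the neonatal composite can score an early neonatal death as event-free and mask a difference in deaths

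*Combined protocol and SAP*

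**What the plan says.** Section 4.2 introduces the neonatal composite with "A composite neonatal morbidity outcome is pre-specified to include one or more of the following before neonatal discharge". Its respiratory component is "severe respiratory distress syndrome (defined as intubation and mechanical ventilation for a minimum of 12 hours". The remaining components are sepsis, transfusion, hypoxic–ischemic encephalopathy, high-grade intraventricular hemorrhage, necrotizing enterocolitis and head cooling. Outside the composite, the neonatal outcomes are any NICU admission, "neonatal intensive care unit admission greater than 48 hours, and neonatal length of stay (days".

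No fetal or neonatal death is in these lists. Specific aim 3 ends its safety outcomes with "side effects (headache, nausea, vomiting, dizziness), and neonatal resuscitation", and Hypothesis 3 likewise goes no further than resuscitation. The only death named as an outcome is "maternal death", a component of the maternal composite in the same section. Fetal demise appears once, as an entry exclusion (3.4.2).

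Enrollment is open from 24 weeks to singleton pregnancies (3.4.1). Section 5.5 specifies intent-to-treat but gives no rule for a death in any neonatal outcome. Section 5.1 expects no missing outcome data on the women and does not mention the baby.

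**The concern.** The trial sets out to judge whether the study drug is safe and has an acceptable balance of risk and benefit, in a population that reaches down to 24 weeks. Death is the most serious neonatal outcome and can prevent a less serious one from being recorded. A composite that leaves it out needs a separate death outcome and a rule for how a death is scored. The plan has neither.

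The rule would then have to be chosen after the data are in, and the choice affects the result. A death before any listed component could be scored as no event, dropped from the denominator, or counted as an event. Length of stay and NICU stay over 48 hours have the same gap. Taken at face value, an early death gives a short stay and no prolonged NICU admission. The documents also do not rule out treating these values as missing.

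**Working it through.** **The plan's own figures.** The plan gives no figure for fetal or neonatal death. Its stated power concerns cesarean delivery only and does not bear on this point. It does reproduce. With 45% v 30.15% (a 33% relative reduction) and 196 per arm after 2% loss, the pooled-variance formula gives z = (0.1485 × √196 − 1.96 × 0.6849) / 0.6768 = 1.09, or 86.2% power, against the stated >85%.

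**How section 4.2 scores each kind of death, read literally.**

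| Case | Neonatal composite | Length of stay, NICU >48 h |
|---|---|---|
| Live birth, a listed component, then death | Event | No rule; a short value if death is early |
| Live birth, death before 12 h of ventilation, no other component | No event | No rule; a favorable value at face value |
| Fetal death in labor | Undefined (no neonatal discharge) | Undefined |

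**Effect on the composite (assumed numbers).** Suppose 20 of 200 babies per arm have a listed component, and one arm has d further deaths with none.

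| Rule for those deaths | d = 2 | d = 4 | Other arm |
|---|---|---|---|
| Scored event-free | 20/200 = 10.0% | 20/200 = 10.0% | 10.0% |
| Dropped | 20/198 = 10.1% | 20/196 = 10.2% | 10.0% |
| Counted as events | 22/200 = 11.0% | 24/200 = 12.0% | 10.0% |

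The first two rules hide the difference or nearly so. Neither makes the arm with more deaths look better.

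**How many pregnancies are at the earliest gestations.** The inputs are the gestational-age table and text in section 5.1.
- Row sum: 13 + 15 + 26 + 39 + 56 + 35 + 57 + 17 + 8 + 2 = 268. The text says 295, so 27 women have no stated gestation.
- 24–28 weeks, per 400: 400 × 13/268 = 19.4. If none of the 27 fall in this band, 400 × 13/295 = 17.6. If all do, 400 × 40/295 = 54.2.
- Under 32 weeks, per 400: 400 × 54/268 = 80.6. The range is 400 × 54/295 = 73.2 to 400 × 81/295 = 109.8.

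**How many deaths (assumed mortality).** The documents give no rate. At an assumed 5–20% in the 24–28 week band:
- On 19.4 pregnancies: 0.97 to 3.88 deaths in both arms together.
- Over the 17.6–54.2 range: 0.88 to 10.85 deaths.
- Deaths at later gestations would be extra. This range does not separate fetal from neonatal deaths.

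**How many misclassified in the composite.** This depends on the unknown share of deaths with no prior listed component. On the base of 19.4 pregnancies, it is none at 0%, 0.49 to 1.94 at 50%, and 0.97 to 3.88 at 100%. Even 1.94 deaths all in one arm move that arm's composite by 1.94/200, about 1 percentage point. The d = 4 column is therefore an extreme on this base: it needs the highest assumed mortality, no prior component in any baby, and complete imbalance.

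**What a death count could show.** For 0 v 4 deaths of 200, the two-sided Fisher p = 2 × C(200,4)/C(400,4) = 0.12. A by-arm count is descriptive.

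**The case against.** The best defense is that a death would not go unseen. A preterm baby who dies within hours would often register as a NICU admission, which section 4.2 lists, or as neonatal resuscitation, which aim 3 names. Section 1.1 promises the "incidence of maternal/neonatal complications associated with use of IMN, to the point of discharge/transfer". Interim reports under 5.2 cover "all outcome variables, adverse events reported and center performance", and 5.3 provides for serious adverse events. Intent-to-treat in 5.5 makes dropping a randomized pregnancy less natural. Babies who die will often have had a listed component first, and deaths will be few.

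Most of this stands. A reader might infer that neonatal deaths would be invisible in this trial, and the documents do not support that. But none of these provisions makes death an outcome analyzed by arm or says how it is scored, and 5.2 puts its emphasis on the primary outcome and maternal safety. Intent-to-treat argues for keeping a fetal death in the denominator but does not say whether it is an event. That a morbidity composite should exclude death by design is hard to maintain when its maternal counterpart includes it.

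A reader might also infer that the composite would favor the arm with more deaths. That would require deaths to displace listed events, and nothing in the documents shows this. Favorable values after an early death are plausible only for length of stay and NICU stay over 48 hours.

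**Conclusion.** The omission is certain on the text: neither death is a listed outcome, and its handling is undefined. Following the composite as written can score an early neonatal death as event-free, and leaves a fetal death in labor without a status. The consequence is masking or dilution of a difference in deaths.

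The size is uncertain and probably small. The estimate of about 1 to 4 deaths at 24–28 weeks, some of them misclassified, rests on an assumed 5–20% mortality. It also assumes that the trial has the same gestational mix as the source cohort. The description of that cohort does not mention selection on the trial's limits for Bishop score, dilation, fetal anomaly or Category III tracing, so the mix may differ. The point is one of definition and does not depend on those numbers. It affects neonatal safety conclusions only, not the cesarean comparison.

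**What to change.** In section 4.2:

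1. Add to the neonatal composite: *intrapartum fetal death or neonatal death before neonatal discharge*. This is the window its other components already use. Section 1.1 speaks of discharge or transfer; whatever is decided for transferred babies should apply equally to every component.
2. State that the denominator is all randomized pregnancies. This is well defined, because all are singletons and fetal demise is excluded at entry.
3. Report fetal deaths and neonatal deaths separately by arm, as descriptive counts.
4. Show those counts beside length of stay and NICU stay over 48 hours, and label any survivor-only values as such. Ranking deaths worst in these two outcomes is an option, but the concern is met without it.

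The cost is one extra abstraction field for research nurses who already abstract outcomes from the records (3.5.5), plus a few sentences. The limitation is that events will be few, so the comparison of deaths is descriptive only. The primary outcome, N = 400 and its power do not change.
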